6.7 Treatment Windows

CBT: For participants randomized to receive CBT, treatment will commence as soon after the last day of baseline PRO-Diary monitoring as therapist/participant schedules will allow. Efforts will be made to complete 1 session per week for 8 consecutive weeks (main treatment sessions) followed by 2 approximately every-other-week maintenance sessions (maintenance sessions). However, flexibility in the scheduling of these sessions will allow for, at a minimum, completion of the 8 main treatment sessions within the 12-week treatment period. If needed, scheduling of >1 session/week, but no more than 2 sessions in a 7-day period is allowable to ensure that the full treatment is delivered in the 12-week treatment period. No treatment sessions will be delivered beyond the 12-week treatment period.

Modafinil: For participants randomized to receive modafinil, treatment will commence the day after the last day of baseline PRO-Diary monitoring, and continue for a period of 12 consecutive weeks. For patients receiving combination therapy, Modafinil will start on or before first day of CBT.

6.8 Participant Compensation

Participants will be compensated \$300 for full completion of the study. For those who do not complete all study assessments, the compensation schedule is noted on the consent form and is as follows:

Baseline Assessment: Participants will receive \$100 for fully completing the baseline REDCap surveys and home monitoring period assessment. For those who do not complete both components of the baseline assessment, participants will receive \$25 for completing REDCap survey measures & \$75 for completing the home monitoring period assessments (minimum 3 days of data).

Week 8 Assessment: Participants will receive \$50 for completing the Week 8 REDCap surveys.

Week 12 Assessment: Participants will receive \$100 for fully completing the Week 12 REDCap surveys and home monitoring period assessment. For those who do not complete both components of the Week 12 assessment, participants will receive \$25 for completing REDCap survey measures & \$75 for completing the home monitoring period assessments (minimum 3 days of data).

Week 24 Assessment: Participant will receive \$50 for completing the Week 24 REDCap surveys.

Participants will be compensated for assessments after each completion; thus, they may be remitted up to four separate payments, after completion of each assessment period.

6.9 SCHEDULE OF ACTIVITIES

Study Activity	Baseline (week -1 to -2)	Weeks 1-7**	Week 8	Weeks 9-11	Week 12	Weeks 13-23	Week 24
Demographics	X						
Medical/Surgical History	X		X		X		X
Interview with a Neurologist for assessment of eligibility	X						
Krupp's Fatigue Severity Scale (FSS)	X						
Patient Health Questionnaire-3	X						
Medication review	X		X		X		X
Baseline urine Pregnancy test if applicable	X						
AE/SAE review (all participants)*	X		X		X		X
Randomization	X						
Modafinil dispensing (for Groups 2 and 3)	X		X				
Study Intervention Administration		X	X	X	X		
Treatment adherence			X		X		
Treatment Utilization Patterns (post-intervention)							X
Excess modafinil destruction (if applicable)					X		
Computer-based self-report measures							
Modified Fatigue Impact Scale (MFIS)	X		X		X		X
EDSS self-report	X						
STOP-BANG questionnaire	X						
RLS Index	X						

Epworth Sleepiness Scale	X		X		X		X
Insomnia Severity Index	X						
Sleep Hygiene Index	X		X		X		X
Patient Health Questionnaire-8	X		X		X		X
Generalized Anxiety Disorder-7	X		X		X		X
Brief Pain Inventory	X		X		X		X
Exercise (Godin)	X		X		X		X
PROMIS Self-Efficacy Scale	X		X		X		X
PROMIS Cognitive Function	X		X		X		X
MSQOL54- Quality of Life Subscale	X		X		X		X
NeuroQoL Ability to Participate in Social Roles & Activities	X		X		X		X
Post-Treatment Questionnaire					X		X
Patient Global Impression of Change					X		X
7-day home monitoring (PRO-Diary) measures							
Physical Fatigue Severity (4x/day)	X				X		
Mental Fatigue Severity (4x/day)	X				X		
Physical Fatigue Impact (4x/day)	X				X		
Mental Fatigue Impact (4x/day)	X				X		
Wake up time (1x/day)	X				X		
Bed time (1x/day)	X				X		
Sleep refreshed (1x/day)	X				X		
Rest breaks (1x/day)	X				X		
Cognitive clarity (1x/day)	X				X		
Cognitive speed (1x/day)	X				X		

Pain Severity (1x/day)	X				X		
Daytime physical activity (continuous)	X				X		

* For Modafinil-treated participants in Group 2 and 3, AE/SAE review will be additionally assessed at the following time intervals:

- 2-4 days after starting Modafinil
- 7-10 days after starting Modafinil

**Activities marked Week 1-7 begin after the baseline assessments, which include a 7-day home monitoring period.

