For Aim 3, using treatment adherence as the dependent variable (continuous outcome), a multiple linear regression power analysis was performed assuming a full model consisting of up to 8 possible predictor variables: treatment group (independent variable of interest), age, gender, EDSS score, baseline fatigue level, baseline activity level, presence of sleep disturbance (yes/no), and depression severity (PHQ-9 Score). Based on a sample size of n=300, we will have 95% power to detect an R-square difference of 0.03 for the test predictor of interest, assuming the R-squared explained by the adjustment variables is at least 0.3.

9.2 Analysis of Study Aims:

Aim 1: Compare the effectiveness of 3 therapies: CBT monotherapy, modafinil monotherapy, and CBT+modafinil combination therapy on patient-reported fatigue impact (primary outcome), fatigue intensity, and fatigability among fatigued individuals with MS. The primary outcome measure will be the mean difference in Modified Fatigue Impact Scale (MFIS) score between 12 weeks and baseline (delta-MFIS), compared between treatment groups. A repeated measures mixed effects model will be applied. The mean difference will also be adjusted for baseline covariates: age, gender, anxiety, pain, and exercise, which were included as covariates based on their established association between fatigue and/or activity in MS. Additional secondary analyses will also evaluate treatment effect on EMA outcome measures of fatigue impact, fatigue intensity, and fatigability.

Aim 2: Test whether depression, sleep disturbances, or MS disability level modify comparative treatment responsiveness across treatment arms in terms of fatigue impact (HTE analyses). Treatment group effect on fatigue impact scores, fatigue intensity, and fatigability among select subgroups, including those with clinically significant depression, progressive MS subtype and higher EDSS scores, and confirmed/suspected sleep disorders not related to poor sleep hygiene, will be evaluated with interaction terms in mixed effects models as above.

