Aim 3: Compare adverse events, side effects, treatment adherence, and patient dropout rates among the three treatment arms and patient subgroups of interest. Descriptive statistics will be used to analyze patterns of adverse events including side effects (incidence, type, severity, and relatedness) and treatment adherence between treatment groups (modafinil vs. CBT vs. combination therapy) throughout the 12-week intervention interval. Adverse event frequency between treatment groups and among subgroups of interest will be evaluated using ANOVA. Multiple linear regression models adjusted for age, gender, EDSS score, baseline fatigue level, baseline activity level, presence of sleep disorder (yes/no), and depression severity (PHQ-8 Score) will be used to determine association between treatment group and treatment adherence (percent usage of prescribed therapy). We also will assess whether degree of treatment effects measured in Aim 1 are related to treatment adherence (e.g. “dose response”).

9.3 Analysis of Exploratory Aims:

Additional analyses modeled as in 9.2 above will also evaluate treatment effect on the difference between 8 week and baseline MFIS scores, to assess whether treatment effects are detectable prior to the 12-week assessment period.

Additional analyses modeled as in 9.2 above will also evaluate treatment effect on the difference between 24 week and baseline MFIS scores, to assess whether treatment effects are detectable following the 12-week assessment period.

Descriptive statistics will be used to summarize clinical treatment utilization patterns between 12-24 weeks, following the 12-week intervention interval.

Analyses modeled as in 9.2 will also be used to evaluate treatment effects on other outcomes at 12 and 24 weeks. We will examine differential treatment effects on changes in the following

factors (assessed via survey): ability to participate in social roles and activities, pain interference, quality of life, and self-efficacy for managing MS symptoms. We will also examine differential treatment effects on changes from baseline to 12 and 24 weeks in the following outcomes that were assessed via survey and/or EMA: pain intensity, perceived cognitive functioning, and pacing behaviors. Treatment group differences in scores on the PGIC measure at 12 and 24 weeks will be examined in models similar to the approach described in 9.2.

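### Aim 3 compares adverse event frequency between arms that are asked about events unequally often, and its dose-response analysis would be partly circular if usage is measured by modafinil quantity

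*Combined protocol and SAP*

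**What the plan says.** The schedule in section 6.9 has an AE/SAE review row for all participants at baseline and Weeks 8, 12 and 24. Its footnote continues: "For Modafinil-treated participants in Group 2 and 3, AE/SAE review will be additionally assessed at the following time intervals". The first interval is "2-4 days after starting Modafinil" and the second is days 7–10. Treatment lasts 12 weeks in every arm (section 6.4).

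For Aim 3, section 9.2 says: "Adverse event frequency between treatment groups and among subgroups of interest will be evaluated using ANOVA". It mentions neither the number of reviews per arm nor the source of each report. Section 7.5 collects AEs at every visit and call, planned or not. Section 6.6 assigns safety assessments to the coordinator, at study visits and in further contacts with the participant, phone calls included. Section 5.3 has separate interventionists deliver the CBT calls.

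On adherence, section 9.2 plans regression models for the "association between treatment group and treatment adherence (percent usage of prescribed therapy", a single measure for all three arms. It adds: "We also will assess whether degree of treatment effects measured in Aim 1 are related to treatment adherence". Section 5.3 lets modafinil participants stay on a dose that works, increase it if relief is insufficient, and reduce it for side effects, out of a supply of up to four 100 mg pills a day. The documents do not define the denominator of percent usage for modafinil.

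**The concern.** Comparing harms and adherence is the declared content of Aim 3. If one arm is asked about symptoms more often than another, a difference in recorded AE frequency mixes harm with frequency of asking, and a reader cannot separate the two. CBT-alone participants have no scheduled AE review between baseline and Week 8, while the other two arms have two such reviews in the first ten days.

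The dose-response analysis has a different problem. If usage means pills taken or share of supply used, the participants who use most include those whose fatigue responded least at lower doses. Usage is then partly a consequence of response. More use could go with worse outcome even if modafinil works.

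**Working it through.** **The plan's own figure.** Section 9.1 says of Aim 3: "using treatment adherence as the dependent variable (continuous outcome), a multiple linear regression power analysis was performed", with 8 predictors and an adjustment R-square of 0.3, and concludes "we will have 95% power to detect an R-square difference of 0.03 for the test predictor of interest" at n=300. Alpha is not stated for Aim 3; I assume 0.05. Then f² = 0.03/(1 − 0.30 − 0.03) = 0.03/0.67 = 0.0448. At n=300, λ = 300 × 0.0448 = 13.4 on 1 and 291 df, and power is 95.5%. The stated 95% is reproduced. At n=200 (two arms of about 100), λ = 8.96 on 1 and 191 df, and power is 84.6%.

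**Counting reviews (section 6.9).** Baseline precedes treatment and Week 24 follows it.

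- CBT alone: Weeks 8 and 12 = 2.
- Modafinil, and combination: days 2–4, days 7–10, Weeks 8 and 12 = 4 each.
- If the 8 + 2 = 10 CBT calls also count: 2 + 10 = 12, 4, and 4 + 10 = 14.

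**Illustration of size.** The following assumptions are mine, not the documents'. True AE rates are equal in all arms. Each AE has one chance of being reported, at the next contact, with probability 2^(−d/h), where d is the delay in days and h, the recall half-life, is 14, 28 or 56 days. Reviews fall on days 56 and 84 for CBT alone, and on days 3, 8, 56 and 84 in the modafinil arms. CBT calls, where counted, are weekly to day 56 and then on days 70 and 84. There are 100 participants per arm and 0.5–1 true AE per person, with Poisson counts.

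For onsets spread over 84 days, mean detection is (h/ln 2) × Σ(1 − 2^(−L/h))/84, where L runs over the gaps between contacts. With h = 28:

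- CBT alone, gaps 56 and 28: 40.4 × (0.750 + 0.500)/84 = 0.601.
- Modafinil, gaps 3, 5, 48 and 28: 40.4 × (0.072 + 0.116 + 0.695 + 0.500)/84 = 0.665.
- Ratio: 0.665/0.601 = 1.11.

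Results for h = 14/28/56:

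| Setting | CBT alone | Modafinil | Ratio, modafinil to CBT | 5% ANOVA rejects |
|---|---|---|---|---|
| Schedule 2/4/4, spread onsets | 0.406/0.601/0.763 | 0.484/0.665/0.805 | 1.19/1.11/1.06 | about 6–12% |
| Schedule 2/4/4, exactly a quarter of onsets in days 0–8 in every arm | 0.349/0.546/0.722 | 0.556/0.714/0.834 | 1.59/1.31/1.16 | about 9–58% |
| CBT calls count, spread onsets | 0.804/0.894/0.945 | 0.484/0.665/0.805 | 0.60/0.74/0.85 | about 11–84% |

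Rejection rates are simulated. With equal detection the rate is 4.8%. In the last row it also reflects the gap between modafinil and combination.

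**Usage.** Measured against a supply of four 100 mg pills a day, steady use at 50, 100, 200 or 400 mg/day scores 50/400 = 12.5%, 25%, 50% or 100%. Each level can be reached under the titration rules in section 5.3. Measured against the participant's own current dose, all four score 100%.

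**The case against.** **Direction.** A reader might infer that the plan favours CBT alone. The documents do not settle this. The coordinator's role in section 6.6 suggests that CBT sessions are not AE reviews, but the same sentence extends safety assessment to further contacts, and section 7.5 includes planned calls. If CBT calls count, CBT alone is asked more often than modafinil alone. What stands is that the arms are unequal on either reading.

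**Size.** A reader might also infer a large bias from the early reviews. That needs AEs to cluster in the first days under CBT alone as well, and nothing in the documents shows this. If early clustering is confined to modafinil starters, the extra reviews record real drug events. With spread onsets on the 2/4/4 schedule the effect is small. The model also ignores spontaneous reports, persistent symptoms and a second chance of report at Week 12. Section 7.5 asks about symptoms experienced while on the study, which should soften the imbalance.

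**Adherence.** The plan does not say that usage means pill quantity, so the circularity is conditional on that choice. It would also be too strong to call the missing rule for combining pills and sessions in the combination arm an error; it is largely missing detail. Nor should total pill counts at 50 and 400 mg/day over 84 days be read as an eightfold range open to one participant. That ignores the advised first-week doses and mixes participants under different limits.

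The extra early contacts may be justified for safety, and nothing here argues against them.

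**Conclusion.** The concern holds as a limitation of Aim 3. Scheduled on-treatment AE review is 2/4/4, or about 12/4/14 if CBT calls count, and the ANOVA in section 9.2 makes no allowance for either. Part of a between-arm difference can therefore reflect frequency of asking. Its sign for CBT versus modafinil depends on a point that the documents leave open.

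The spread-onset figures are the main case: ratios of 1.06–1.19 on the schedule, or 0.60–0.85 if calls count. They illustrate an assumed recall model and are not estimates for this trial. On scheduled reviews alone, modafinil and combination are balanced at 4 each.

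The dose-response problem follows from the titration rules if usage is scored by pill quantity or share of supply. The primary MFIS comparison is not affected by either issue.

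**What to change.** 1. State whether CBT calls are AE contacts. Keep every safety contact and the all-source AE comparison. Flag each AE by source. Beside the all-source result, report a between-arm comparison limited to AEs elicited at the Week 8 and Week 12 reviews, with the same questions and look-back in all arms. Interpret CBT-versus-modafinil differences in light of both.
2. Score modafinil adherence as the percentage of treatment days on which any was taken, and CBT adherence as sessions completed of those prescribed. Compare the first between Groups 2 and 3 and the second between Groups 1 and 3. Present any modafinil-versus-CBT adherence contrast descriptively.
3. In the dose-response analysis, use days taken or sessions completed within each component, not pill quantity or share of supply. Report it as a non-randomised association, since these measures also arise after baseline.

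The work is SAP text, a source flag on the AE form, one look-back wording, and a days-taken item in the existing Week 8 and 12 adherence assessment.

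There are costs. The common-review comparison can miss early transient events and openly reported ones, and participants already questioned in days 2–10 may answer differently at Week 8, so it supplements the all-source comparison and does not fully equalise ascertainment. Open-label reporting differences remain. Days taken relies on recall. Each component adherence comparison has about 200 participants and about 85% power at an R-square difference of 0.03, against 95% at n=300, and the single three-arm adherence test is given up.

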7. ASSESSMENTS

7.1.1 Primary Outcome Assessments (see also section 7.1.3)

The Modified Fatigue Impact Scale (MFIS, primary outcome measure)^{1,2}: is a patient-reported 21-item validated measure of fatigue impact based on patients' recent personal experience as it relates to physical, cognitive, and psychosocial functioning. The MFIS has been shown to be sensitive to changes secondary to interventions. Scores range from 0-84. Higher scores indicate more fatigue.

7.1.2 Secondary/exploratory outcome assessments, effect modifier measures, screening measures (see also section 7.1.3)

Self-reported Expanded Disability Status Scale (SR-EDSS)³: is a validated self-report version of the clinician-administered EDSS; scores on the SR-EDSS correspond highly with clinician-rated EDSS.

STOP-Bang Questionnaire: The STOP-Bang is a validated, 8-item screening instrument that assesses characteristics known to confer risk for OSA, and form the acronym "STOP-BANG" (Snoring, Tiredness, Observed apneas, high blood Pressure, BMI, Age, Neck circumference, Gender).⁴ Item scores (1/0) are based on yes/no answers. Scores ≥ 3 indicate elevated risk for sleep apnea.

Krupp's Fatigue Severity Scale (FSS)⁵ – I/E criterion: The FSS is a validated, 9-item instrument that measures the impact of fatigue on multiple outcomes, with a physical focus. Prior studies have shown acceptable internal consistency and stability over time, and sensitivity to change that correlates with the subject's clinical improvement. Many if not most past studies on MS-related fatigue have used the FSS.

Epworth Sleepiness Scale (ESS)⁶: The ESS is an 8-item questionnaire that asks about the likelihood of dozing in variably sedentary situations. This commonly used measure of subjective sleepiness, or sleep propensity, is reliable, internally consistent, and validated against objective polysomnographic measures. A score ≥ 10 suggests excessive sleepiness.

Insomnia Severity Index (ISI)^{7,8}: The Insomnia Severity Index (ISI) is a 7-item questionnaire with 5-point Likert scale responses designed to assess the nature, severity, and impact of insomnia in adults. Scores of 15 or higher reflect moderate clinical insomnia.

Sleep Hygiene Index (SHI)⁹: The Sleep Hygiene Index is a 13-item self-report measure designed to assess the practice of sleep hygiene behaviors. Each item is rated on a five-point scale ranging from 0 (never) to 4 (always). Total scores range from 0 to 52, with a higher score representing poorer sleep hygiene.

Restless Legs Syndrome Diagnostic Index (RLS-DI)^{10,11}: is a 10-item questionnaire designed to improve diagnostic decision making in suspected cases of RLS. This instrument incorporates essential diagnostic criteria with additional supportive criteria to rule out false positive cases, which can occur in patients with MS. A score of +11 yields a 93% sensitivity and 96% specificity to diagnose RLS.

The Patient Health Questionnaire –8 (PHQ-8)¹²: assesses frequency of 8 depressive symptoms in the past 2 weeks. It has been validated in MS and provides clinical cut-points ranging from no depression to severe depression (range 0-24).

Patient Health Questionnaire-2^{12,13} plus item 9/i from the PHQ-9¹⁴ (PHQ-3) – I/E criterion: assess the frequency of 3 depressive items in the past two weeks. The PHQ-2 has been validated as a depression screen and item 9/i from the PHQ-9 is used to assess for suicidal ideation.

The Brief Pain Inventory (BPI)^{15,16}: assesses both pain intensity (4 items) as well as pain interference in multiple life domains (7 items) and has demonstrated good psychometric characteristics, including validity, in MS.

The Generalized Anxiety Disorder – 7 (GAD-7)^{12,17}: is a commonly used anxiety measure that assess 7 symptoms of anxiety in the past 2 weeks, and provides clinical cut-points for anxiety severity (scores range 0 – 21).

The Godin Leisure-Time Exercise Questionnaire¹⁸: is a brief, 4-item measure of the frequency and intensity of exercise during “a typical week” that has been frequently used in MS clinical research and has even been used to validate accelerometer measures of physical activity in MS.

Neuro-QoL Ability to Participate in Social Roles & Activities 8-item Short Form^{19,20}: is an 8-item measure of a person’s ability to participate in various social roles and activities across a range of social domains (home/family, recreation). Raw scores range from 8-40, with higher scores indicating better ability to participate. T scores, with a Mean=50 and SD=10 can be calculated for comparison to a normative sample of individuals with neurological conditions. This measure has been validated in MS.

Patient Reported Outcomes Measurement Information System (PROMIS) Self-Efficacy for Managing Symptoms Short Form 8a^{21,22}: is an 8-item measure developed to assess confidence or self-efficacy for managing symptoms and is meant to be used across clinical conditions. Raw scores range from 8-40 and T-scores have a Mean=50, SD=10; higher scores indicate greater self-efficacy.

Patient Reported Outcomes Measurement Information System (PROMIS) Cognitive Abilities Short Form 8a: is an 8-item measure that assesses perceived cognitive function. Raw scores range from 8-40 and T-score have a Mean = 50, SD=10; higher scores indicate greater cognitive functioning. This measure has demonstrated good reliability and validity in MS²³.

Patient Global Impression of Change (PGIC)²⁴: is a commonly-used single-item measure that assesses perceived overall change across multiple life domains since beginning treatment. Higher scores indicate greater improvement since treatment was initiated.

Quality of Life Subscale from the Multiple Sclerosis Quality of Life-54 Instrument²⁵⁻²⁷: contains two items that assess perceived general quality of life. The possible range is 0-100 with higher values indicating higher quality of life.

Post-Treatment Questionnaire; contains questions about the patient intent to continue the treatment they received during the 1st 12 weeks (on a clinical basis), their reasons for doing so, and means/barriers to obtaining this treatment. This questionnaire will be administered at 12 and 24 weeks.

Ecological Momentary Assessment (EMA) measures: Eleven EMA items were created (adapted from validated surveys) to assess fatigue, fatigue impact, sleep, pacing, cognitive function, and pain. EMA items are as follows:

1) Physical Fatigue (four times daily):

What is your level of physical (bodily) fatigue right now? on a scale of 0 – 10, where 0 = No Fatigue and 10 = Extremely Severe Fatigue.

2) Mental Fatigue (four times daily):

What is your level of mental (brain) fatigue right now? on a scale of 0 – 10, where 0 = No Fatigue and 10 = Extremely Severe Fatigue.

3) Physical Fatigue Interference (four times daily):

How much is your physical fatigue interfering with what you are doing right now? on a scale of 0 – 10, where 0 = no interference and 10 = totally interfering; not able to do what I want because of fatigue. Slight change in wording for bedtime: How much did your physical fatigue interfere with what you were doing leading up to your bedtime? On a scale of 0 – 10, where 0 = no interference and 10 = totally interfered, was not able to do what I wanted because of fatigue.

4) Mental Fatigue Interference (four times daily):

How much is your mental fatigue interfering with what you are doing right now? on a scale of 0 – 10, where 0 = no interference and 10 = totally interfering; not able to do what I want because of fatigue. Slight change in wording for bedtime: How much did your mental fatigue interfere with what you were doing leading up to your bedtime? On a scale of 0 – 10, where 0 = no interference and 10 = totally interfered, was not able to do what I wanted because of fatigue.

5) Wake Up Question (administered once daily):

What time did you wake up this morning?

6) Go To Bed Question (administered once daily):

What time did you go to bed [last night]?

7) Sleep (administered once daily at wake):

How refreshed did you feel when you woke up this morning? on a scale from 0-10 where 0=Totally Unrefreshed (not at all rested) and 10=Totally Refreshed (restored, revitalized, ready to start the day).

8) Rest Breaks (administered once daily at bedtime)

Today, how often have you taken rest breaks to do your activities? On a scale where 0 = Not at all, 5 = Sometimes, and 10 = Always.

9) Cognitive Clarity (administered once daily at bedtime)

Today, on average, my thinking was: Please rate on a scale of 0-10 where 0 = very clear to 10 = very foggy

10) Cognitive Speed (administered once daily at bedtime)

Today, on average, my thinking was: Please rate on a scale of 0 – 10, where 0 = very fast to 10 = very slow

11) Pain (administered once daily at bedtime) Today, what was your average level of pain? On a scale where 0 = no pain at all and 10 = worst pain imaginable

Covid Impact Survey: The COVID-19 Impact Survey was designed to assess impacts of COVID-19 on participants that could have an effect on study outcomes. It was adapted from the COVID-19 Exposure and Family Impact Survey (CEFIS), developed by The Center for Pediatric Traumatic Stress. Part 1 consists of 22 items that measure the participants' "exposure" to COVID-19 and related events. The Exposure Score is a count of "yes" responses and may range from 0 to 22. Part 2 consists of 13 items that measure the impact of COVID-19. 10 items use a five-point Likert scale rating impact on participant's and family's life; 1 item uses an 11-point distress scale. Higher scores denote more negative impact / higher distress. The Impact Score (sum of items 23-35) may range from 12 to 70. Part 3 is an open-ended question so that participants can expand upon their experiences and add effects of COVID not covered in the other questions.

